9.1.1.2 Serious adverse event

Once it is determined that a study participant experienced an AE, the seriousness of the AE must be determined. An SAE must meet 1 or more of the following criteria:

- Death
- Life-threatening
(Life-threatening does not include a reaction that might have caused death had it occurred in a more severe form.)
- Significant or persistent disability/incapacity
- Congenital anomaly/birth defect (including that occurring in a fetus)

- Important medical event that, based upon appropriate medical judgment, may jeopardize the patient or study participant and may require medical or surgical intervention to prevent 1 of the other outcomes listed in the definition of serious

(Important medical events may include, but are not limited to, potential Hy's Law [see Section 9.2], allergic bronchospasm requiring intensive treatment in an emergency room or at home, blood dyscrasias that do not result in inpatient hospitalization, or the development of drug dependency or drug abuse.)

- Initial inpatient hospitalization or prolongation of hospitalization

(A patient admitted to a hospital, even if he/she is released on the same day, meets the criteria for the initial inpatient hospitalization. An emergency room visit that results in admission to the hospital would also qualify for the initial inpatient hospitalization criteria. However, emergency room visits that do not result in admission to the hospital would not qualify for this criteria and, instead, should be evaluated for 1 of the other criteria in the definition of serious [eg, life-threatening adverse experience, important medical event].

Hospitalizations for reasons not associated with the occurrence of an AE [eg, preplanned surgery or elective surgery for a pre-existing condition that has not worsened or manifested in an unusual or uncharacteristic manner] do not qualify for reporting. For example, if a study participant has a condition recorded on his/her medical history and later has a preplanned surgery for this condition, it is not appropriate to record the surgery or hospitalization as an SAE, since there is no AE upon which to assess the serious criteria. Please note that, if the pre-existing condition has worsened or manifested in an unusual or uncharacteristic manner, this would then qualify as an AE and, if necessary, the seriousness of the event would need to be determined.)

9.1.1.2.1 Anticipated serious adverse events

The following Anticipated SAEs, fatigue, infection and headache are anticipated to occur in the population studied in this protocol at some frequency that is independent of drug exposure.

This information does not change the investigator's obligation to report all SAEs (including Anticipated SAEs) as detailed in Section 9.1.2.3.

9.1.1.3 Adverse events of special interest

An AE of special interest is any AE that a regulatory authority has mandated be reported on an expedited basis, regardless of the seriousness, expectedness, or relatedness of the AE to the administration of a UCB product/compound.

Potential Hy's Law, defined as $\geq 3 \times \text{ULN}$ ALT or AST with coexisting $\geq 2 \times \text{ULN}$ total bilirubin in the absence of $\geq 2 \times \text{ULN}$ ALP, with no alternative explanation for the biochemical abnormality, must ALWAYS be reported to UCB as an AE of special interest (ie, without waiting for any additional etiologic investigations to have been concluded). Follow-up information should then be reported if an alternative etiology is identified during investigation and monitoring of the study participant.

9.1.1.4 Adverse events of interest

For rozanolixizumab, AEs of interest that require immediate reporting to UCB are:

- Severe headache
- Moderate to severe diarrhea
- Moderate to severe abdominal pain
- Moderate to severe vomiting

These events should be reported to UCB within 24h, regardless of seriousness, by completing the eCRF. If the electronic system is unavailable for more than 24 hours, then the site will use the paper SAE data collection tool (see Section [9.1.2.3](#) for the reporting process).

Additional assessments that may be required in case of AEs of interest are presented in [Table 5-2](#).

9.1.2 Procedures for reporting and recording adverse events

The study participant will be given the opportunity to report AEs spontaneously. A general prompt will also be given at each study visit to detect AEs. For example:

“Did you notice anything unusual about your health (since your last visit)?”

In addition, the investigator should review any self-assessment procedures (eg, e-diary cards) employed in the study.

9.1.2.1 Description of adverse events

When recording an AE, the investigator should use the overall diagnosis or syndrome using standard medical terminology, rather than recording individual symptoms or signs. The eCRF and source documents should be consistent. Any discrepancies between the study participant's own words on his/her own records (eg, e-diary card) and the corresponding medical terminology should be clarified in the source documentation.

Details for completion of the Adverse Event eCRF (including judgment of relationship to IMP) are described in the eCRF Completion Guidelines.

- Mild: An event that is easily tolerated by the participant, causing minimal discomfort and not interfering with everyday activities
- Moderate: An event that causes sufficient discomfort and interferes with normal everyday activities
- Severe: An event that prevents normal everyday activities. An AE that is assessed as severe should not be confused with an SAE. Severe is a category utilized for rating the intensity of an event; and both AEs and SAEs can be assessed as severe.
- An event is defined as ‘serious’ when it meets at least 1 of the predefined outcomes as described in the definition of an SAE, NOT when it is rated as severe (eg, a severe AE may be either serious or not serious, depending on whether these criteria are also met).

9.1.2.2 Rule for repetition of an adverse event

An increase in the intensity of an AE should lead to the repetition of the AE being reported with:

- The outcome date of the first AE that is not related to the natural course of the disease being the same as the start date of the repeated AE, and the outcome of “worsening”
- The AE verbatim term being the same for the first and repeated AE, so that the repeated AE can be easily identified as the worsening of the first one

9.1.2.3 Additional procedures for reporting serious adverse events

If an SAE is reported, UCB must be informed within 24h of receipt of this information by the site. The primary mechanism for reporting an SAE to UCB will be the eCRF (using the eCRF SAE page). If the electronic system is unavailable for more than 24 hours, the investigator must forward to UCB (or its representative) a duly completed paper SAE data collection tool provided by UCB, even if the data are incomplete, or if it is obvious that more data will be needed in order to draw any conclusions (see contact information for SAE reporting listed in the Serious Adverse Event Reporting section at the front of the protocol). The site will enter the SAE data into the electronic system as soon as it becomes available.

The investigator SAE Report form must be completed in English.

It is important for the investigator, when completing the SAE data collection tool, to include the assessment as to a causal relationship between the SAE and the IMP administration. This insight from the investigator is very important for UCB to consider in assessing the safety of the IMP and in determining whether the SAE requires reporting to the regulatory authorities in an expedited manner.

Additional information (eg, autopsy or laboratory reports) received by the investigator must be provided within 24h. All documents in the local language must be accompanied by a translation in English, or the relevant information included in the same document must be summarized in the investigator SAE data collection tool.

The investigator is specifically requested to collect and report to UCB (or its representative) any SAEs (even if the investigator is certain that they are in no way associated with the IMP), up to 30 days from the end of the study for each study participant, and to also inform participating study participants of the need to inform the investigator of any SAE within this period. Serious AEs that the investigator thinks may be associated with the IMP must be reported to UCB regardless of the time between the event and the end of the study.

Upon receipt of the SAE data collection tool, UCB will perform an assessment of expectedness of the reported SAE. The assessment of the expectedness of the SAE is based on the IB.

After the study is completed at a given site, the electronic data collection tool will be taken off-line to prevent the entry of new data or changes to existing data.

If a site receives a report of a new SAE from a study participant or receives updated data on a previously reported SAE after the electronic data collection tool has been taken off-line, then the site can report this information on a paper SAE form.

9.1.2.4 Immediate reporting of adverse events

The following AEs must be reported immediately using the SAE data collection tool according to the procedure in Section 9.1.2.3:

- SAE: AE that the investigator classifies as serious by the above definitions regardless of causality
- Suspected transmission of an infectious agent via a medicinal product
- AE of special interest (see Section 9.1.1.3)
- AE of interest (see Section 9.1.1.4)
- Confirmed LTBI, active TB, and NTMBI (see Section 9.3.6)

9.1.3 Follow up of adverse events

An AE should be followed until it has resolved, has a stable sequelae, the investigator determines that it is no longer clinically significant, or the study participant is lost to follow up. This follow-up requirement applies to AEs, SAEs, and AEs of special interest; further details regarding follow up of PDILI events is provided in Section 9.2.1.4.

If an AE is ongoing at the end of the study for a study participant, follow up should be provided until resolution/stable level of sequelae is achieved, or until the investigator no longer deems that it is clinically significant, or until the study participant is lost to follow up. If no follow up is provided, the investigator must provide a justification. The follow up will usually be continued for 8 weeks after the study participant has discontinued his/her IMP.

Information on SAEs obtained after clinical database lock will be captured through the Patient Safety (PS) database without limitation of time.

9.1.4 Pregnancy

If an investigator is notified that a study participant has become pregnant after the first intake of any IMP, the investigator must immediately notify UCB's PS department by providing the completed Pregnancy Report and Outcome form (for contact details see SAE reporting information at the beginning of this protocol). The study participant should be withdrawn from the study as soon as pregnancy is known (by positive pregnancy test), and the following should be completed:

- The study participant should return for a PEOT Visit.
- The study participant should immediately stop the intake of the IMP as instructed at the PEOT Visit.
- An FV should be scheduled 8 weeks after the study participant has discontinued her IMP.

The investigator must inform the study participant of information currently known about potential risks and about available treatment alternatives.

The pregnancy will be documented on the Pregnancy Report and Outcome form provided to the investigator. The progression of the pregnancy and the eventual birth (if applicable) must be followed up using the Pregnancy Report and Outcome form in which the investigator has to

report on the health of the mother and of the child. Every reasonable attempt should be made to follow the health of the child for 30 days after birth for any significant medical issues. In certain circumstances, UCB may request that follow up is continued for a period longer than 30 days. If the study participant is lost to follow up and/or refuses to give information, written documentation of attempts to contact the study participant needs to be provided by the investigator and filed at the site. UCB's PS department is the primary contact for any questions related to the data collection for the pregnancy, eventual birth, and follow up.

In cases where the partner of a male study participant enrolled in a clinical study becomes pregnant, the investigator or designee is asked to contact the study participant to request consent of the partner via the Partner Pregnancy Consent form that has been approved by the responsible IRB/IEC and should be available in the investigator site file. In case of questions about the consent process, the investigator may contact the UCB/contract research organization (CRO) contract monitor for the study. The investigator will complete the Pregnancy Report and Outcome form and send it to UCB's PS department (for contact details see SAE reporting information at the beginning of this protocol) only after the partner has agreed that additional information can be captured and has provided the signed Partner Pregnancy Consent form. UCB's PS department is also the primary contact for any questions related to the data collection for the partner pregnancy, eventual birth, and follow up.

A pregnancy becomes a SAE in the following circumstances: miscarriage, abortion (elective or spontaneous), unintended pregnancy after hormonal contraceptive failure (if the hormonal contraceptive was correctly used), ectopic pregnancy, fetal demise, or any congenital anomaly/birth defect of the baby. Those SAEs must be additionally reported using the investigator SAE data collection tool.

9.1.5 Suspected transmission of an infectious agent via a medicinal product

For the purposes of reporting, any suspected transmission of an infectious agent via a medicinal product should be considered as an SAE; such cases must be reported immediately, recorded in the AE module of the eCRF, and followed as any other SAE. Any organism, virus, or infectious particle (eg, prion protein transmitting transmissible spongiform encephalopathy), pathogenic or nonpathogenic, is considered an infectious agent.

9.1.6 Overdose of investigational medicinal product

Excessive dosing (beyond that prescribed in the protocol and including overdose ie, >10% above [REDACTED]) should be recorded in the eCRF. Any SAE or nonserious AE associated with excessive dosing must be followed as any other SAE or nonserious AE. These events are only considered AEs or SAEs if there are associated clinical signs and symptoms or if the act of taking the excess medicine itself is an AE or SAE (eg, suicide attempt).

9.1.7 Safety signal detection

Selected data from this study will be reviewed periodically to detect as early as possible any safety concern(s) related to the IMP so that investigators, clinical study participants, regulatory authorities, and IRBs/IECs will be informed appropriately and as early as possible. A DMC will be responsible for monitoring safety data during the study. Further details are provided in Section 14.7.

The Study Physician or medically qualified designee/equivalent will conduct an ongoing review of SAEs and perform ongoing SAE reconciliations in collaboration with the PS representative.

As appropriate for the stage of development and accumulated experience with the IMP, medically qualified personnel at UCB may identify additional safety measures (eg, AEs, vital signs, laboratory or ECG results) for which data will be periodically reviewed during the course of the study.

9.1.8 Suicidality

At Screening, the investigator will query each study participant if he/she has a lifetime history of suicide attempt (including an active attempt, interrupted attempt, or aborted attempt) or suicidal ideation in the past 6 months. A full C-SSRS “Lifetime recent” assessment will be performed only when the study participant has a positive response to this query. This scale will be assessed by trained study personnel. When suicide attempt or suicidal ideation is confirmed by a positive response (Yes) to either Question 4 or Question 5 of the C-SSRS, the study participant must be excluded and immediately referred to a Mental Healthcare Professional.

At each clinical visit, the investigator must query the suicidal ideation since the last visit. A full C-SSRS “Since last visit” assessment will be performed only when the study participant has a positive response to this query. When suicide attempt or suicidal ideation is confirmed by a positive response (Yes) to either Question 4 or Question 5 of the C-SSRS, the study participant must be withdrawn and immediately referred to a Mental Healthcare Professional. Details of the case must be documented by the investigator (principal investigator or investigator physician, not site staff conducting the C-SSRS) and provided to UCB via the SAE reporting process.

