5.2 Schedule of study assessments

The schedule of study assessments are provided in [Table 5-1](#).

PUBLIC COPY
This document cannot be used to support any marketing application and any extensions or variations thereof.

Table 5-1: Schedule of study assessments

Assessments	Visit	1 Scr ^b	24-Week Treatment Period (Part 1)												52-Week Additional Treatment Period (Part 2 - Optional) ^a		8-Week Observation Period (Optional)			
			2 BL	3	4	5	6	7	8	9	10 14 18 22	11 15 19 23	12 16 20 24	13 17 21 25	Additional Visits numbered sequentially	26 PEOT	27	28	29 FV	
	Week	-5 to -2	1	2	3	4	5	6	7	8	9	10 13 17 21	11 14 18 22	12 15 19 23	Every 4 weeks	Weekly in between site visits	25 or 77	27 or 79	29 or 81	32 or 84
Visit type ^c	S	S	S	S	S	S	H ^d	S	H ^d	S	H ^d	H ^d	H ^d	H ^d	S	H ^d	H ^d	H ^d	S	
Written informed consent ^e	X	X																		
Demographic data ^e	X	X																		
Verification of inclusion and exclusion criteria ^e	X	X																		
Withdrawal criteria			X	X	X	X	X	X	X	X	X	X	X	X	X	X	X	X	X	
Medical history update ^e	X	X																		
Prior and concomitant medication	X	X ^f	X	X	X	X	X	X	X	X	X	X	X	X	X	X	X	X	X	
Concomitant medical procedures	X	X ^f	X	X	X	X	X	X	X	X	X	X	X	X	X	X	X	X	X	
Vital signs ^g	X	X	X	X	X	X	X	X	X	X	X	X	X	X	X	X	X	X	X	

Table 5-1: Schedule of study assessments

Assessments	Visit	1 Scr ^b	24-Week Treatment Period (Part 1)												52-Week Additional Treatment Period (Part 2 - Optional) ^a		8-Week Observation Period (Optional)			
			2 BL	3	4	5	6	7	8	9	10 14 18 22	11 15 19 23	12 16 20 24	13 17 21 25	Additional Visits numbered sequentially	26 PEOT	27	28	29 FV	
	Week	-5 to -2	1	2	3	4	5	6	7	8	9	10 13 17 21	11 14 18 22	12 15 19 23	Every 4 weeks	Weekly in between site visits	25 or 77	27 or 79	29 or 81	32 or 84
Body weight		X	X ^f												X ^h		X			X
Recording of AEs		X	X ^f	X	X	X	X	X	X	X	X	X	X	X	X	X	X	X	X	X
Query for suicidality ⁱ		X	X ^f	X	X	X	X	X	X	X	X	X	X	X	X	X	X	X	X	X
Fatigue scale			X ^f			X				X					X ^j		X			X
CIDP PRO Instrument			X ^f			X				X					X ^j		X			X
PGIS			X ^f			X				X					X ^j		X			X
PGIC			X ^{fk}			X				X					X ^j		X			X
Full physical examination		X	X ^f																	X
Brief physical examination				X	X	X	X		X		X				X		X			

Table 5-1: Schedule of study assessments

Assessments	Visit	1 Scr ^b	24-Week Treatment Period (Part 1)												52-Week Additional Treatment Period (Part 2 - Optional) ^a		8-Week Observation Period (Optional)			

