^h Body weight is collected every 6 months during Treatment Period Part 2 starting at first visit in this period and will be used to select the correct volume for dose infusion from these timepoints.

ⁱ A full C-SSRS assessment will be performed only when the study participant has a positive response to the suicidal ideation query. If a study participant has active suicidal ideation as confirmed by the answer “Yes” to Question 4 or Question 5 of the C-SSRS assessments, the study participant will be excluded or withdrawn from the study and immediately referred to a Mental Healthcare Professional.

^j Only performed every 24 weeks.

^k Not required for study participants who had a Screening Visit.

^l The full neurological examination includes a fundoscopy. In addition to the FV, a full neurological examination should be performed for any study participant who experiences severe headache (refer to Section 5.2.1 and Table 5-2).

^m Assessment to be performed every 12 weeks (Weeks 25, 37, 49 and 61).

ⁿ Serology includes hepatitis C virus (HCV)-antibodies (Ab)+, hepatitis B virus antibodies (HBsAg and HBcAb), human immunodeficiency virus antibodies (HIV1 and HIV2).

^o In case of immediate entry from the parent study, the serum pregnancy test from the parent study should not be older than 5 weeks prior to entry into this CIDP04 study and the urine pregnancy test done at Visit 2 must both be negative before dosing. In case of gap period between the parent study and entry in CIDP04, a serum test will be performed at Visit 1 (Screening). Pregnancy testing will consist of urine testing at dosing visits during the Treatment Period Part 1, monthly urine testing during Treatment Period Part 2 and at each visit during the Observation Period for women of childbearing potential. A positive urine pregnancy test must be confirmed using a serum pregnancy test. Note that the final urine pregnancy test of the study should be no longer than 90 days after the final dose of IMP.

^p The IGRA test will be performed in a central laboratory.

^q Tuberculosis signs and symptoms Questionnaire must be done at least every 12 weeks.

^r Self-administration may be performed by study participant under the supervision of the home nurse after full training.

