9. Study participant has active suicidal ideation as indicated by a positive response (“Yes”) to either Question 4 or Question 5 of the “Since Last Visit” version of the Columbia Suicide Severity Rating Scale (C-SSRS) at Baseline Visit (Visit 2),

or

Study participant has a lifetime history of suicide attempt (including an active attempt, interrupted attempt, or aborted attempt), or has suicidal ideation in the past 6 months as indicated by a positive response (“Yes”) to either Question 4 or Question 5 on the Screening C-SSRS.

The study participant should be referred immediately to a Mental Healthcare Professional and must be withdrawn from the study.

10. Study participant has a known hypersensitivity to any components of rozanolixizumab.
11. Study participant intends to have a live vaccination during the course of the study or within 7 weeks following the final dose of rozanolixizumab.
12. Study participant has an ongoing serious adverse event (SAE) or a medical condition in the parent study that the investigator considers to put the study participant at a significantly increased risk of participating in CIDP04.
13. Study participant has any planned elective surgery due to occur during the study dosing period which in the opinion of the investigator could interfere with study procedures.

6.2.1 Additional exclusion criteria for study participants with a gap period between the parent study and entry in CIDP04

14. Study participant has a current diagnosis or has a history of Type 1 or Type 2 diabetes mellitus and/or hemoglobin A1c level >6.0%.
15. Study participant with IgM paraproteinemia.
16. Study participant has known IgM-mediated neuropathy (eg, multifocal motor neuropathy).
17. Study participant has clinical or known evidence of associated systemic diseases that might cause neuropathy, including but not limited to connective tissue disease, Lyme disease, Castleman's disease and systemic lupus erythematosus, malignant plasma cell dysplasia, or treatment with agents that might lead to neuropathy (eg, amiodarone therapy).
18. Study participant on an average dose less than 0.4g IgG/kg/month over the past 4 months.

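### An on-study suicide attempt with a negative ideation query cannot reach the withdrawal and referral that Protocol 9.1.8 sets for attempts, and Section 6.4 does not list an attempt

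*Protocol*

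**What the plan says.** Protocol 9.1.8 has two paragraphs. The Screening paragraph asks about attempts and recent ideation: "At Screening, the investigator will query each study participant if he/she has a lifetime history of suicide attempt" is how it begins. The on-study paragraph asks about ideation alone: "At each clinical visit, the investigator must query the suicidal ideation since the last visit". In both, the full C-SSRS follows only a positive answer to the query.

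The on-study consequence has a condition and an action. The condition is "When suicide attempt or suicidal ideation is confirmed by a positive response (Yes) to either Question 4 or Question 5 of the C-SSRS". The action is that "the study participant must be withdrawn and immediately referred to a Mental Healthcare Professional". The investigator must also document the case and send it to the sponsor through the SAE process.

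Protocol Table 5-1 lists the item under the broader label "Query for suicidality". Its footnote i then narrows it: "A full C-SSRS assessment will be performed only when the study participant has a positive response to the suicidal ideation query". The footnote continues "If a study participant has active suicidal ideation as confirmed by the answer" Yes to Question 4 or 5, and again calls for exclusion or withdrawal and referral. SAP 10.4.3 repeats the ideation gate and plans listings only.

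Protocol 6.4 has one suicidality item, the second under mandatory permanent discontinuation of IMP. It covers active ideation shown by Question 4 or 5 and asks for immediate referral. Exclusion criterion 9 in Protocol 6.2 treats an attempt as a ground of its own: "Study participant has a lifetime history of suicide attempt (including an active attempt, interrupted attempt, or aborted attempt".

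**The concern.** The on-study rule in 9.1.8 names a suicide attempt, but each step leading to it is built around ideation. If the query never asks about an attempt, and the scale that would confirm one is opened only by a positive ideation answer, the rule can miss an event it was written to cover.

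What is at stake is a participant-safety rule during weekly dosing that can last up to 76 weeks (24 in Part 1 plus 52 in Part 2). For an attempt outside the ideation route, whether IMP is stopped depends on judgement under general provisions, and no on-study text requires the referral. No efficacy or safety analysis is affected.

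**Working it through.** No probability or effect size is involved. The check follows the on-study decision path through the text and then looks for any other rule that would catch the event.

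**Path in 9.1.8 and Table 5-1 footnote i**

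1. Query: ideation since the last visit. Attempts are not named, although the Screening query in the same section names them.
2. Gate: the full C-SSRS is done only after a positive answer. SAP 10.4.3 says the same.
3. Confirmation: Yes to Question 4 or 5.
4. Action: withdrawal and immediate referral.

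**Cases**

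| On-study event | Query | Question 4 or 5 | Reaches step 4? |
|---|---|---|---|
| Attempt, ideation reported and endorsed | positive | Yes | Yes |
| Attempt, ideation denied at the query | negative | not asked | No |
| Attempt, some ideation reported | positive | No to both | No, if this combination can occur |

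The second row follows from the protocol's wording alone. The third needs knowledge of what Questions 4 and 5 contain. Footnote i, exclusion criterion 9 and 6.4 use them as ideation items, whereas 9.1.8 also uses them to confirm an attempt. The documents do not reproduce the C-SSRS, so the third row is a possibility and no more.

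**Count of numbered items in 6.4**

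- must be withdrawn from the study: 2
- must permanently discontinue IMP: 5
- may be discontinued from IMP: 3
- may be withdrawn from the study: 2

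Total 2 + 5 + 3 + 2 = 12, of which 2 + 5 = 7 are mandatory. Items naming suicidal ideation: 1 of 12 (1 of 7 mandatory). Items naming a suicide attempt: 0 of 12 (0 of 7 mandatory). The count only confirms the omission.

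**Other on-study routes**

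- Protocol 9.1.2 gives a general adverse event prompt at each visit. An attempt can meet the SAE criteria of 9.1.1.2, and 9.1.6 gives an attempt by overdose as an example of an adverse event or SAE. Section 9.1.2.3 requires the sponsor to be told within 24 hours, and 9.1.7 provides for Study Physician review. These provisions concern detection, reporting and review.
- Under mandatory IMP discontinuation in 6.4, item 1 (interfering illness) and item 3 (sponsor or regulator request) could apply. Once judged to apply they compel a stop, but they depend on that judgement and carry no mental-health referral.
- Protocol 13.1 tells the investigator to act at once, outside the protocol if need be, against an immediate hazard to a participant. That permits both a stop and a referral but prescribes neither by name.

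No other current section sets a stop and referral for an on-study attempt.

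**The case against.** The strongest reply is that the gap is small and already surrounded by safeguards. It needs an attempt since the last visit together with a denial of ideation to the investigator. The scheduled item carries a label broad enough that nobody is barred from asking about behaviour. Exclusion criterion 9 keeps out people with a lifetime attempt and itself requires referral at entry. An attempt would very likely be reported as an SAE, and 13.1 would support immediate action. The protocol does not list suicidality among its adverse events of special interest (9.1.1.3) or of interest (9.1.1.4).

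The reply also guards against three stronger readings that a reader might infer:

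- *That 9.1.8 makes withdrawal and referral compulsory after any attempt.* It does not. The duty applies when the attempt or ideation is confirmed by Question 4 or 5. The word attempt may even have been carried over from the Screening paragraph.
- *That Questions 4 and 5 cannot register an attempt.* The documents do not show the instrument, so this cannot be asserted.
- *That the protocol leaves an on-study attempt without any response.* The reporting duties, the general items of 6.4 and 13.1 say otherwise.

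What stands of the reply is the limit on size. It does not remove the defect. The table label is defined by its footnote and by 9.1.8 as an ideation query. The entry criterion does not operate on study. The remaining routes allow a response without prescribing both elements of it. If the word attempt was carried over by accident, the protocol has no on-study rule for attempts at all, and the same edit is needed.

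**Conclusion.** The point holds in limited form. As written, an on-study attempt with a negative ideation query cannot reach the stop and referral that 9.1.8 attaches to attempts, and 6.4 offers no attempt criterion in its place. An attempt with No to Questions 4 and 5 may miss them too, subject to the content of an instrument that is not shown.

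The conclusion rests on reading the on-study query as 9.1.8 and footnote i define it, not as the row label might suggest. Confidence is high for the ideation-only query and for the omission in 6.4, and lower for the Question 4 and 5 branch. The documents state no frequency of on-study attempts, so the number of participants affected cannot be estimated. The change is worth making because it is cheap and repairs a safety rule that cannot reach an event it names.

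**What to change.** - **Protocol 9.1.8 and Table 5-1 footnote i:** make the on-study query cover an actual, interrupted or aborted attempt as well as ideation, and trigger the full C-SSRS on either.
- **Protocol 9.1.8 and 6.4 (mandatory permanent IMP discontinuation, item 2):** name any such attempt as a stop with immediate referral to a mental healthcare professional, independent of Questions 4 and 5.
- **Same two sections:** use one term for the consequence. At present 9.1.8 speaks of withdrawal while 6.4 places the item under IMP discontinuation.
- **SAP 10.4.3:** match the description of the query.

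The cost is one added question in an existing query and wording changes. Because a mandatory stop is altered, they belong in a protocol amendment with the approvals described in Protocol 15.5. No visit, instrument or analysis is added.
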